Proprotein convertase subtilisin/kexin type 9 (PCSK9) inhibitors, by modifying LDL receptors, have been shown to dramatically lower LDL. There is robust evidence that lowering LDL cholesterol is beneficial in atherosclerotic disease, due to plaque-stabilizing effects. The FOURIER and ODYSSEY studies showed that patients randomized to PCSK9 inhibition had dramatic LDL reduction and a lower overall incidence of stroke (1.2 versus 1.6% of patients over three years). The GLAGOV study showed that, compared to placebo, evolocumab (Repatha) decreased coronary artery plaque volume. GLAGOV also demonstrated a linear relationship between LDL cholesterol reduction and plaque volume regression. However, these findings do not provide adequate evidence that Repatha reduces the risk of ICAD stroke. FOURIER and ODYSSEY did not adjudicate the etiology of stroke and, for the stroke outcome, they included cardioembolic and lacunar strokes, which typically account for up to 50% strokes. The risk reduction from a PCSK9 inhibitor like Repatha would primarily be for patients with large artery atherosclerosis, such as ICAD. As a result, the absolute risk reduction seen in those studies does not represent the potential of Repatha in a patient population at risk for stroke.

A.3. Repatha

Repatha is an FDA-approved PCSK9 inhibitor shown to reduce the risk of cardiovascular events, including myocardial infarction, stroke, and coronary revascularization. Repatha is a patient-administered subcutaneous injection that is well tolerated. Common side effects include flu-like symptoms, cough, back pain, and dizziness. Further information can be obtained at: (https://www.pi.amgen.com/~/media/amgen/repositorysites/pi-amgen-com/repatha/repatha_pi_hcp_english.pdf).

A.4. Stenosis and Plaque Atheroma Volume Measured on vwMRI

We will measure both stenosis and atheroma volume to have two primary outcomes with validated biomarker potential. Stenosis is measured using WASID criteria.¹³ Atheroma volume is either directly measured or inferred by measuring the area of entire vessel (the outer wall boundary area) on an axial slice and subtracting the lumen area. In a study of middle cerebral artery ICAD, the atheroma volume on vwMRI was larger in the 26 symptomatic patients compared to the 35 asymptomatic patients (12.9±3.1 mm² vs. 8.2±3.6 mm², p<0.001). A second study enrolled 139 patients with moderate to severe middle cerebral artery atherosclerosis, who contributed 112 culprit and 53 non-

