All drug compliance records will be kept current and will be made available for inspection by regulatory agency inspectors. Study drug will be given to patient at the baseline visit, and preferably at 6 month intervals thereafter. Instructions for shipping study drug to patients are provided in the appendix.

B.9. Study Timeline

There are two in-person study visits (baseline and 78 week follow-up) when patients will undergo vwMRI, approximately 60 minutes long, with a simultaneous clinical evaluation by a study investigator physician and blood draw. Every 2-4 months, the study coordinator will determine medication adherence, adverse events, or patient-reported recurrent stroke (see **Figure 1**).

	Screen/ Baseline	Day 1	Day 60	Day 120	Day 180	Day 240	Day 320	Day 480	Day 546
Informed Consent	Х								
Medical History/Current medications	х		х	х	х	Х	х	х	х
Vitals	Х								Х
Review CTA or MRA ¹	х								
Vessel wall MRI		Х							Х
Pregnancy test	Х								
Creatinine	Х								Х
Lipid panel	Х								Х
Lipoprotein (a)	Х								Х
Apolipoprotein B	Х								Х
Physical exam	Х								Х
Neurological exam	Х								х
NIHSS	Х								Х
Modified Rankin Scale	х								Х
Stroke adjudication			Х	Х	Х	Х	Х	Х	Х
Adverse event determination			х	Х	х	Х	х	х	х
Serious adverse events			Х	Х	Х	Х	Х	Х	Х

Figure 1: Schedule of Activities

1. To confirm ICAD of a major intracranial artery

B.10. Study Duration

- Estimated duration of research (study start to final study deliverable): 2 Years / 6 Months
- Estimated duration of first patient enrolled to last patient out: 2 Year / 0 Months
- Estimated duration for Amgen to supply study drug: 2 Year / 0 Months

C. Study Endpoints

C.1. Primary Endpoints

The primary endpoints are nominal change in the stenosis and percent atheroma volume (PAV) of cerebrovasculture arteries from baseline to week 78. We will use measure stenosis and PAV on vessel wall MRI (vwMRI), which evaluates all arteries from the aortic arch to the distal intracranial vasculature in a single scan. The primary endpoints will be analyzed for both: 1) all intra- or extracranial arteries that have at least 25% stenosis, and 2) seperately for the intracranial arteries. Stenosis and PAV will be measured using standard methodology.

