C.1.a. Primary endpoint measurement: All vwMRIs are on a 3T scanner with a 20- or 32-channel head coil and gadolinium. The field of view is from the aorta to the top of the skull. Sequences include the following for Siemens scanners and equivalents for Phillips and GE:

Sequence	3D ToF	DWI	3D FLAIR	3D MPRAGE	PD SPACE DANTE	3D SWI	T1 SPACE DANTE	T2 SPACE DANTE
Contrast (gadolinium)	Pre	Pre	Pre	Pre	Pre	Pre	Pre/Post	Post

DANTE = Delay Alternating with Nutation for Tailored Excitation (for blood suppression); DWI = Diffusion Weighted Imaging (Tensor technique); GRE = Gradient Recalled Echo; MPRAGE = Magnetization Prepared Rapid Acquisition Gradient recalled Echo; PD = proton density; SPACE = Sampling Perfection with Application optimized Contrasts using different flip angle Evolution; SWI = susceptibility weighted imaging (with quantitative susceptibility mapping); ToF = Time-of-Flight

At the completion of patient enrollment, two neuroradiologists will examine all vwMRIs in three separate viewing sessions to prevent viewer fatigue. They will be given a rater sheet directing them to record findings in the brain and all major vessels of the cerebrovasculature, including:

- a) Stenosis: will be identified by the luminal imaging component of the vwMRI protocol (MR angiography of the head and neck). Stenosis will documented on the NIH Stroke CDE "Vessel Imaging Angiography"²⁵ for all cerebrovasculature vessels from the aorta to distal intracranial vessels. Any vessel with >25% stenosis qualifies for computation of this composite outcome.
- b) Percent atheroma volume (PAV): We will use MRI-PlaqueView (VPDiagnostics, Seattle, WA) to measure PAV in the aortic arch, cervical carotid, cervical vertebral and all major intracranial arteries. MRI-PlaqueView is a powerful application that allows identification of (a) vessel lumen and outer wall (OW), (b) atheroma (both calcified and lipid rich). PAV is measured on the cross-sectional slice with the highest % stenosis. PAV = Σ(OWarea Lumenarea)/ΣOWarea × 1

C.2. Secondary endpoint 1

Secondary endpoint 1 is post-contrast plaque enhancement for intracranial arteries and intraplaque hemorrhage for the cartotid artery, which are determined by two experienced neuroradiologist raters. If there is disagreement, then a third rater serves as a tie-breaker. The signal intensity characteristics of both endpoints have been standardized in prior literature.

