We will fit a mixed effects linear regression model, specifically a LOESS smoothing curve, to change in stenosis/PAV and on-treatment LDL-C, HDL-C, and lipoprotein(a). We will also use a multivariable linear regression model with the outcome of the primary endpoints, adjusted for covariates that could be confounders such as age, gender, smoking, statin use/dose and relevant medical comorbidities. The primary endpoints will also be compared to an assumed value of 0% change in stenosis and PAV that would correspond to optimal medical management without a PCSK9 inhibitor. Although, some studies have suggested statin therapy can reduce carotid atherosclerosis, no such effect is known for ICAD. For this analysis, we will use linear mixed effects model to detect differences in the stenosis and PAV endpoints between patients taking Repatha or the presumed historical control values of 0% change. For the secondary endpoints, we will use logistic and linear regression depending on the nature of the variable and use the primary predictors of on-treatment LDL-C, HDL-C, and lipoprotein(a). For the exploratory endpoint of recurrent stroke, we will use the above mentioned methods as well as a Cox proportional hazards model for the endpoint of recurrent stroke with the observed rate in this study compared to controls matched according to degree to stenosis of the index artery. Due to differences in arterial structure and flow dynamics, there may be a more significant plaque reduction in certain intracranial vessels. We anticipate subgroup analyses, for example comparing change in stenosis or PAV in the middle cerebral artery versus the vertebral artery.

D.2. Power Analysis

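### PAV, a primary endpoint, is read on one slice with no rule for the week-78 slice and no blinding to visit order, and the ICC behind the 0.51% detectable effect is not stated

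*Combined protocol and SAP*

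**What the plan says.** - **Slice rule.** C.1.a item b: "PAV is measured on the cross-sectional slice with the highest % stenosis". No visit is named. The formula beside it is a sum, "PAV = Σ(OWarea Lumenarea)/ΣOWarea × 1", with no visible statement of what is summed. A.4 allows a slice-based measure: "Atheroma volume is either directly measured or inferred by measuring the area of entire vessel (the outer wall boundary area) on an axial slice".
- **Lesion qualification.** C.1.a item a admits any vessel above 25% stenosis, again without naming the visit.
- **Reading.** C.1.a: "At the completion of patient enrollment, two neuroradiologists will examine all vwMRIs in three separate viewing sessions". The sessions are split to limit fatigue. Nothing says that readers are blind to which scan came first.
- **Timing.** B.10: "Estimated duration of first patient enrolled to last patient out: 2 Year / 0 Months" and "Estimated duration of research (study start to final study deliverable): 2 Years / 6 Months". The schedule in B.9 puts the follow-up scan at day 546.
- **Comparator.** The study has a single arm. D.1: "The primary endpoints will also be compared to an assumed value of 0% change in stenosis and PAV".
- **Power.** D.2 uses 150 patients, 4 sites each, SD 4%, two-sided 0.05 and an expected 1% reduction. It gives 0.51% as the smallest effect detectable with 80% power. It mentions an intra-class correlation (ICC) without a value, and an effective sample size of 800 to 1200.

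**The concern.** Picking the most extreme slice on one scan and measuring the same place again later invites regression to the mean. Stenosis and PAV both depend on the lumen seen in one session (C.1 describes vessel wall MRI as a method "which evaluates all arteries from the aortic arch to the distal intracranial vasculature in a single scan"). A lumen read too small at baseline can raise both values and make that slice more likely to be chosen. At week 78 the error need not recur, and PAV then seems to regress. A concurrent control arm would share the effect and cancel it, but a fixed 0% cannot. The same holds for a reader who knows which scan is the later one. The expected effect is only 1%, so a few tenths of a point matter. If the rule is settled only after images are seen, it cannot be told apart from a post hoc choice.

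**Working it through.** **1. Reading time.** Two years is about 730 days, and each patient needs 546. To meet B.10, enrolment must close by day 730 - 546 = 184. The first week-78 scan falls at about day 546. Read literally, only baseline scans exist at the planned reading, and readers would know that they are baseline scans.

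**2. The plan's 0.51%.** Detectable effect = (1.960 + 0.842) × SD × sqrt((1 + 3 × ICC)/(4N)).
- N = 150, SD 4, ICC 0: 2.8016 × 4/sqrt(600) = 0.457%.
- Setting the result to 0.51 gives 1 + 3 × ICC = 600 × (0.51/11.206)² = 1.243, so ICC = 0.081 (0.073 to 0.089 allowing for rounding) and an effective n of 483.
- An effective n of 800 or 1200 from 150 × 4 = 600 change values would need 1 + 3 × ICC = 0.75 or 0.50, so ICC = -0.083 or -0.167. No non-negative ICC gives more than 600.

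| SD 4% | ICC 0.08 | ICC 0.3 | ICC 0.5 |
|---|---|---|---|
| Detectable effect, 150 patients | 0.51% | 0.63% | 0.72% |
| Detectable effect, 105 completers (30% lost) | 0.61% | 0.75% | 0.86% |
| Power for 1%, 105 completers | 99.6% | 96% | 90% |

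**3. Bias if a baseline-picked slice is reused.** This is a simulation with no true change, and every input is assumed: 6 or 10 slices per lesion, a linear or quadratic peaked profile 10 points deep, and the slice picked on measured stenosis with the same error-to-depth ratio as PAV. Errors are correlated within a scan and independent between scans. Entries are the mean apparent change in PAV points.

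| Error correlation | Slice error SD 1 | SD 2 | SD 3 | SD 4 |
|---|---|---|---|---|
| 0 | 0 | 0 | 0 | 0 |
| 0.1 | -0.05 to -0.09 | -0.12 to -0.22 | -0.22 to -0.38 | -0.37 to -0.49 |
| 0.3 | -0.16 to -0.27 | -0.40 to -0.65 | -0.73 to -1.09 | -1.14 to -1.54 |
| 0.5 | -0.28 to -0.45 | -0.69 to -1.09 | -1.22 to -1.80 | -1.90 to -2.54 |

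The right-hand columns are less plausible. If D.2's 4% is the SD of change, slice error cannot exceed 4/sqrt(2) = 2.8 points. At 2.83 the bias is -0.67 to -1.01 at correlation 0.3 and -1.14 to -1.67 at 0.5.

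Re-picking on each scan, or choosing one location from both scans together, gives a mean within about 0.04 of 0 in every setting with equal error at the two visits. With error SD 3 at baseline and 2 at week 78 (correlation 0.3 to 0.5), joint choice leaves roughly -0.3 to -0.7 and re-picking about 0 to -0.45.

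**4. Consequence for the test against 0%.** Chance of a significant reduction with an inactive drug = Φ(bias/SE - 1.96), with SE = 4 × sqrt((1 + 3 × ICC)/420) for 105 completers. SE is 0.309 at ICC 0.5 and 0.217 at ICC 0.08.

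| Size of downward bias | ICC 0.5 | ICC 0.08 |
|---|---|---|
| 0 | 2.5% | 2.5% |
| 0.1 | 5% | 7% |
| 0.2 | 9% | 15% |
| 0.4 | 25% | 45% |

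**The case against.** The strongest reply is that the bias needs a reading that the plan does not state. Readers are to examine every scan, and the slice sentence, applied scan by scan, means picking again each time. With equal error at both visits that gives no mean bias. This stands: nothing says that a baseline slice is reused. It does not remove the point, because the opposite reading is equally open and the literal reading time favours baseline-first selection. The reference to all scans does suggest that a later reading was meant.

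Second, stenosis comes from the MR angiography component and PAV from vessel-wall software, so their errors may be only weakly correlated. This also stands. At correlation 0.1 and slice error SD 1, the bias is under 0.1 point. A bias of -0.4 needs roughly correlation 0.3 with error SD 2, or a comparable combination.

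Third, the 0% comparison is one of several D.1 analyses, and a uniform shift would not alter the slope on LDL-C. That is true, but D.2 powers the study on exactly this comparison.

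A reader might also infer that the summed formula contradicts the single-slice sentence. The documents do not support that. The formula is visibly damaged in the extracted text, an index may be lost, and A.4 permits inference from a slice. The range of the sum is undefined, which is less than a contradiction.

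**Conclusion.** The point holds as a gap in the definition of a primary endpoint, with a conditional route to a false positive. It should be fixed before reading; confidence is moderate. What the documents establish is that there is no slice rule for week 78, no blinding to visit order, a reading time that literally precedes all follow-up scans, and a fixed comparator that cannot absorb a selection effect. The size is not established. It runs from 0 to beyond one point, depending on an assumed error correlation, slice error and slice count, so the false-positive rates of 25 to 45% illustrate one corner of that range and are not a forecast.

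Two stronger conclusions are tempting. One is that the trial will show a spurious reduction; the plan does not say that the baseline slice is reused. The other is that 0.51% is wrong or that the study is underpowered. D.2 omits the ICC and does not tie its 4% SD to a single-slice measure, and its 800 to 1200 cannot be an effective number of change values. But an ICC of about 0.08 reproduces 0.51%, and power for a 1% reduction stays at about 90% or more with 105 completers up to ICC 0.5 at SD 4%.

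**What to change.** Before any image is read:

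1. **C.1.a.** Move the reading to after the last week-78 scan. Read each patient's two scans as a pair, with readers blind to visit order. Apply one symmetric rule to both visits, for the slice and for qualification at more than 25% stenosis. One suitable wording: *For each qualifying lesion, one matched location is chosen from both scans together, without knowledge of visit order, and is measured on both.* State what the sum in the PAV formula runs over.
2. **D.2.** State the ICC behind 0.51% and its source, or replace the single figure by the range in the first table of the working. Correct the 800 to 1200, since 150 patients with 4 sites give at most 600 change values.

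Renaming the measure and computing PAV over all slices are options, not requirements.

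**Cost and limits.** No new scans are needed. The final contours remain 150 × 4 × 2 = 1,200 per reader (840 for 105 completers). The added work is matching candidate slices by location on both scans, and the documents do not describe a tool for that. Reading is concentrated after last patient out, where B.10 leaves at most about 6 months (2 years 6 months less 2 years), and less if study start precedes first enrolment. The change limits slice-selection bias. It does not remove it if image error differs between visits, and it does not reduce variance.

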culprit lesions.²² The combination of stenosis + atheroma burden + luminal area produced an odds ratio of 3.99 (95% CI: 1.74-9.13, p=0.001) for culprit plaque. The GLAGOV study showed that PCKS9 inhibition reduced the percent atheroma volume of coronary arteries over a 78 week treatment period.²³ With atheroma volume now established as a viable biomarker, vwMRI is the optimal test to monitor it and stenosis, both for ICAD and in other locations of the cerebrovasculature, such as the carotid arteries, cervical vertebral arteries, and aortic arch.

A.5. Impact

The result of this study will be a dataset that lays the foundation for a randomized controlled trial of Repatha in ICAD patients. The data collected in this study will allow us to optimize a future clinical trial designed to demonstrate a reduction in stroke risk, ultimately making more efficient and economical progress towards our ultimate research goal of preventing stroke with Repatha. While we are proposing future studies to reduce ICAD stroke risk, it should be noted that our study will also evaluate the potential for Repatha to decrease cerebrovasculature stenosis and plaque burden, which would be a compelling primary prevention indication.

B. Approach

B.1. Study Hypothesis

We hypothesize that inhibition of PCSK9 with Repatha in patients with moderate to severe intracranial atherosclerosis will reduce validated biomarkers of stroke risk (stenosis and percent atheroma volume). To answer our hypothesis, we propose a single arm study of Repatha in 150 patients with a prior history of ischemic stroke and ICAD causing at least 50% stenosis of a major intracranial artery in the Circle of Willis ("index artery").

B.2. Study Design

We will enroll 150 ICAD patients with a prior history of ischemic stroke. Patients will be enrolled at up to 8 medical centers in North America. All patients will receive Repatha for 78 weeks and will have an MRI before beginning study medication and a comparison MRI immediately after completing study medication.

B.3. Investigational Treatment

The investigational treatment is Repatha 140 mg administered subcutaneously with a single-dose pre-filled pen syringe every 2 weeks for a total of 39 treatments. Dose modification is not allowed.

B.3.a. Inclusion Criteria

- Adult patients, ≥ 18 years of age

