
C.2.a. Secondary endpoint 1 measurement:

a) ICAD post-contrast plaque enhancement (PPE): is a dichotomous variable evaluated on the T1 pre- and post-gadolinium sequences, with multiplanar reconstruction so the ICAD can be seen in cross section.²⁶ PPE is defined by placing a region-of-interest over areas of gadolinium enhancement in ICAD to evaluate if it is equal to or exceeds the signal intensity of the pituitary infundibulum, as previously described.²⁷

- b) Carotid intraplaque hemorrhage (IPH): MPRAGE positive plaque is defined as voxels with at least 2-fold signal intensity compared to sternocleidomastoid muscle as previously described. MPRAGE positive plaques can be reliably identified. Kappa values for inter- and intra-rater reliability for detection of MPRAGE positive plaque were 0.806 and 0.818 respectively (very good agreement).^{28,29}
- c) MRA Flow Dynamics (**MFD**): We will measure MFD using accepted quantitative MRA methodology. The VERiTAS study provided prospective confirmation of the importance of MFD as a biomarker of stroke risk for patients with ICAD. Given that MFD can easily be measured in our vwMRI protocol, we will acquire the data required for its quantification.

C.3. Secondary endpoint 2

To better understand the mechanism of Repatha's effect on intra- and extracranial atherosclerosis, we will measure the endpoint of change in cholesterol markers [LDL-C, HDL-C, lipoprotein (a), apolipoprotein B, and triglyceride level]. The change in cholesterol markers will be correlated with the primary and secondary study endpoints on vwMRI. Cholesterol values will be measured at the baseline and comparison MRIs, which are 78 weeks apart. If standard of care lab values are available within 30 days of the study visit, they can be used in place of the study lab value. An additional exploratory outcome that we will measure is the composite endpoint of "recurrent stroke," which encompasses new patient-reported symptomatic ischemic stroke, transient ischemic attack, or asymptomatic strokes that emerge between MRIs.

C.3.a. Secondary endpoint 2 measurement:

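### Recording plaque enhancement only as yes/no at the infundibulum cut-off discards graded change that the same region-of-interest reading could supply

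*Combined protocol and SAP*

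**What the plan says.** PPE is the first component of secondary endpoint 1 (C.2 and C.2.a). It "is a dichotomous variable evaluated on the T1 pre- and post-gadolinium sequences". The measurement rule is: "PPE is defined by placing a region-of-interest over areas of gadolinium enhancement in ICAD", and the purpose is "to evaluate if it is equal to or exceeds the signal intensity of the pituitary infundibulum". Two neuroradiologists make the call, and C.2 adds: "If there is disagreement, then a third rater serves as a tie-breaker". The support offered for the definition is that it follows earlier literature.

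For secondary endpoints, D.1 says "we will use logistic and linear regression depending on the nature of the variable", with on-treatment LDL-C, HDL-C and lipoprotein(a) as the main predictors. A binary PPE therefore goes to logistic regression. C.3 adds that changes in lipid markers will be correlated with the vessel wall MRI endpoints.

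No section plans a plaque-to-infundibulum ratio, a percent signal change or a graded score. None says how change in PPE between visits is coded, or how a plaque that is negative at baseline is handled. The primary endpoints, stenosis and percent atheroma volume (PAV), are by contrast analysed as continuous change. The power section (D.2) covers those two only.

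**The concern.** The yes/no call is a signal ratio cut at 1. Cutting it has two effects on a before-and-after endpoint:

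- A positive plaque whose signal falls but stays at or above the infundibulum is recorded as unchanged. As an illustration, a fall from 1.6 to 1.05 times the infundibulum counts as nothing, while a fall from 1.01 to 0.99 counts as a full conversion.
- A plaque that is negative at baseline can stay negative or turn positive. It cannot register improvement, however much its signal falls.

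Two uses of the data suffer. The lipid regressions lose precision. The planning value also drops: section A.5 says the dataset is to lay the ground for a randomised trial, and a yes/no record cannot supply the mean and SD of enhancement change that such planning would want.

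**Working it through.** **No figure in the plan to reproduce.** The documents give no prevalence, effect size, correlation or power for PPE, so every PPE input below is an assumption. From the documents: 150 patients in a single arm (B.1), 25–30% withdrawal (D.2, D.3), two-sided 0.05 (D.2). Completers: 150 × 0.70 = 105 to 150 × 0.75 = 112.5. I use 108.

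**1. Loss in the planned kind of analysis.** Suppose the log ratio is normal, a share p of plaques is positive, and c is the matching cut-off on the standard normal scale. For a weak predictor, a binary outcome at one time point keeps the following share of the information in the continuous outcome:

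φ(c)² / [p(1 − p)]

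| Positive share p | φ(c) | Information kept | Equivalent of 108 completers |
|---|---|---|---|
| 50% | 0.3989 | 0.1592/0.25 = 64% | 69 |
| 30% (or 70%) | 0.3477 | 0.1209/0.21 = 58% | 62 |
| 20% | 0.2800 | 0.0784/0.16 = 49% | 53 |
| 10% | 0.1755 | 0.0308/0.09 = 34% | 37 |

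The maximum is at p = 50%, hence at most about 64%. This applies to enhancement at a single visit.

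**2. Loss in a pre-post comparison (illustrative; not a planned test).** Assumptions: 108 completers, one plaque each, bivariate-normal log ratios, a true reduction of 0.25 SD, and correlation r between visits. For the ratio, a paired t test has SD of change √[2(1 − r)] and noncentrality 0.25 × √108 / SD of change:

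- r = 0.3: SD 1.183, noncentrality 2.20, power 59%
- r = 0.5: SD 1.000, noncentrality 2.60, power 73%
- r = 0.7: SD 0.775, noncentrality 3.35, power 91%

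For yes/no I simulated McNemar's test (40,000 runs per cell). In each range the lower figure is the exact version and the upper the large-sample version.

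| r | Ratio | Yes/no, 50% positive | Yes/no, 30% positive | Yes/no, 20% positive |
|---|---|---|---|---|
| 0.3 | 59% | 31–36% | 25–31% | 20–27% |
| 0.5 | 73% | 36–42% | 29–37% | 22–31% |
| 0.7 | 91% | 44–53% | 36–46% | 28–37% |

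Hand check at r = 0.7 and 50% positive: about 18.1% of plaques go from positive to negative and 8.2% the other way. That is 19.5 against 8.9 of 108, so z ≈ (19.5 − 8.9)/√28.4 ≈ 2.0. This sits at the 1.96 threshold, so power is about one half, as the table shows.

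**The case against.** **The intensities may not exist as data.** A reader might infer that both signals are already measured for every plaque at every visit. The text does not go that far. The region of interest is placed over areas that enhance, so none is defined for a plaque that does not enhance, and no section says that numbers are written down. This stands: the fix needs a placement rule and some extra reading.

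**The power contrast is not what this plan loses.** McNemar's test is not planned, and the size of the gap depends on which version is used. This also stands. The information figure in step 1 is closer to the D.1 regression; step 2 only illustrates.

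**More power for a pre-post shift is not evidence of a drug effect.** With one arm, any drift between scans would be picked up too, and D.1 assumes an untreated value (0% change) only for stenosis and PAV. This stands, and it limits how a mean change in the ratio may be reported.

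**The cut-off is literature-based and a ratio is noisy** across up to 8 centers and three scanner makes. The first half is a reason to keep the yes/no result. The second applies to both forms, since the yes/no call is the same ratio cut at 1. With measurement error added at both visits (r = 0.7, 30–50% positive), power was 84% against 31–37% at an error SD of 0.3 between-plaque SDs, and 35% against 14–17% at 1.0.

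**Other inferences the documents do not support.** They do not call PPE the study's marker of plaque activity; carotid intraplaque hemorrhage and flow dynamics are listed beside it. Nor do they say that near-cut-off plaques cause the tie-breaker reads: the third rater is used for any disagreement.

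**Conclusion.** The point holds in limited form. C.2.a(a) makes PPE binary, D.1 then sends it to logistic regression, and nothing elsewhere keeps the graded signal. In a single-time regression, the yes/no form keeps at most about 64% of the information, and 34% if only 10% of plaques are positive. In an illustrative pre-post comparison, power is about 59–91% for the ratio against about 20–53% for yes/no. Both results assume normal log ratios; the second also assumes one plaque per patient, 108 completers, a 0.25 SD reduction, correlation 0.3–0.7 and 20–50% positive. The direction of the loss follows from the definition; its size cannot be fixed from the documents.

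A reader might conclude that the study will miss a treatment effect on enhancement. The documents do not support that: PPE is secondary and unpowered, and a single arm with no untreated value for PPE could not establish such an effect on either scale. Stenosis and PAV are unaffected. This is a low-priority improvement.

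**What to change.** Amend C.2.a(a), D.1 and the rater sheet before the central reads:

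- Add fields for the plaque and infundibulum region-of-interest intensities on post-contrast T1, for each rater at both visits.
- Place the plaque region at the same location at both visits, whether or not the plaque enhances, so that baseline-negative plaques and those that stop enhancing still have a value.
- Average the two raters' log ratios and analyse the change by linear regression on the D.1 lipid predictors.
- Report the mean change and its SD descriptively, stating that no untreated value is available for comparison.
- Keep the literature-based yes/no PPE, with its tie-breaker, alongside.

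Cost: no new scan, rater or patient. C.1.a has the scans read centrally once enrollment is complete, so fields added beforehand cover every baseline and follow-up scan. The price is some extra region placement and recording, mainly for non-enhancing plaques, and a ratio that is less familiar than the yes/no definition and carries scanner and site noise.
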